4. WORK PROPOSED

A. AIM 1: To Test the Hypothesis that a High Protein Diet Reduces Body Weight and Alters the Pattern of Postprandial Gut Hormone Release in Obese Patients.

Rationale: High protein intake has been associated with reduced caloric intake, and meal replacements are an effective strategy for weight loss and weight maintenance in obese subjects.⁽⁴⁾ The primary objective of this study is to evaluate whether the high protein diets based on 1 gram of protein per pound of lean body mass will improve weight loss in comparison to a standard protein diet based on 0.5 gram of protein per pound of lean body mass. In all arms of the study, bioelectrical impedance will be used to determine the protein requirement at the level of 0.5 or 1 gram per pound of lean body mass. The prescribed calories will be the same on all meal replacement weight loss plans. Weight loss will be the primary outcome. Secondary variables will be satiation as measured using a standard questionnaire, bioelectrical impedance analysis, transient elastography, 16S rRNA sequencing and shotgun metagenomics. A third variable will be multi satiety hormone responses as measured before and after a meal.

The study described below is also unique in its design in that in the same subjects we will assess the changes in gut hormone release and the microbiome (Aims 2 and 3). This is the first study to investigate the effects of meal composition on satiety in connection with the microbiome. The result of this study will guide future clinical trials on weight loss with high protein diet in subjects.

Recruitment: Subjects will be recruited through the use of IRB-approved flyers which will be distributed in the primary care and subspecialty clinics. Online advertisement on ClinicalTrials.gov will also be used to disseminate information about this study to make an outreach effort that spans the entire community. In addition, those patients that are being evaluated as part of our MOVE program, a national weight management program designed by the VA NCP, would be provided with information regarding the study.

Approximately 200 healthy volunteers age 30 years and older between BMI of 27 to 40 kg/m² will be able to take part in this study. Patients must fulfill all of the following conditions or characteristics in order to be considered for study enrollment:

Inclusion criteria:

- a. Age 30 years and older at screening.
- b. BMI of 27 to 40 kg/m² inclusive.
- c. Subjects must be in good health as determined by medical history, physical examination, and screening clinical laboratory including chemistry panel and CBC.
- d. Must have stable smoking habits (or be non-smokers) for at least 6 months prior to screening and agree not to intend to change such habits during the course of the study.

- e. Subjects requiring the regular use of any prescription medication may be admitted to the study providing the dose is stable.
- f. Subjects must sign the VA Greater Los Angeles Healthcare System Institutional Review Board-approved written informed consent prior to the initiation of any study specific procedures or randomization.

Exclusion Criteria:

- g. Weight stability: Subjects reporting weight change of >3.0 kg in the month prior to screening.
- h. Any subject who has been on a very low calorie diet (<800 kcal/day) for a period of 4 months or more in the 12 months prior to screening, or who has lost >10 kg in the 6 months prior to screening.
- i. Any subject who has a history of diabetic gastroparesis or gastric emptying disorder.
- j. Use of any other investigational drug(s) within 8 weeks prior to screening.
- k. Abnormal laboratory parameters: Serum creatinine >1.6 mg/cL; Liver function tests, ALT, AST, Bilirubin results >2.0 times the upper limit of normal; Triglycerides >500 mg/dL; total cholesterol >350 mg/dL; TSH outside of normal range.
- l. Subjects who drink >1 alcoholic beverage per day.
- m. Has an implanted cardiac defibrillator.

Pregnant women or women likely to become pregnant during the course of the study may not participate in this study. Female subjects must not be able to conceive by reason of surgery, radiation, 1 year past the onset of menopause, or an approved method of contraception. No vulnerable subjects will be included in the study.

Procedures:

i. Study Design: This randomized controlled study will assign approximately 200 subjects (100 each) to the following arms (Appendix 1): 1) High protein diet group based on 1 gram of protein per pound of lean body mass, and 2) Standard protein diet group as control based on 0.5 gram protein per pound of lean body mass with same calories. All participants will meet with a registered dietitian, physician or nurse practitioner to assist them with their diet efforts in all the arms. In the study, the percent energy from fat will be held constant at 30% and the differences in the diets relate only to the protein and carbohydrate contents (30% protein and 40% carbohydrate, and 15% protein and 55% carbohydrate respectively). At the initial visit patient will not be calorie restricted but will have standardization of their nutritional macronutrient intake based on their group randomization. At the 2 week visit patient will then begin a 1500 calorie restricted diet with the same macronutrient composition (ie. 30% protein and 40% carbohydrate, and 15% protein and 55% carbohydrate respectively for the high and standard protein groups).

ii. Number of Subjects: Approximately 200 healthy volunteers age 30 years and older with a BMI between 27 to 40 kg/m² will be able to take part in this study.

iii. Estimated Study Duration: Accrual period is 3-4 years; anticipated dropout rate is 20%; and total study duration is approximately 5 years (taking into account data analysis).

iv. Subject Eligibility: Subjects will be assigned an enrollment number after signing the informed consent form. The subjects will complete all the screening tests and procedures as listed. When a subject completes the screening tests and procedures, the subjects will be assigned a randomization number. Subjects will be randomized into one of the two diet groups as described in Appendix 1.

The practitioner at screening will obtain each subject's date of birth, sex, race, medical history, current medications, and smoking and alcohol history. The physician will perform complete physical examinations. Height will be measured using a standardized stadiometer, while the subject stands

erect with feet together and head level; height will be measured to the nearest 0.5 cm. Weight will be measured to the nearest 0.25 lbs using a balanced scale. BM will be calculated as weight in kilograms divided by the square of the height in meter. Waist and hip circumferences will be measured in the standing position. The subject should be wearing unrestricting undergarments with a hospital gown being optional. Waist circumference will be measured at the level midway between the lateral lower rib margin and the iliac crest. Hip circumference will be measured at the level of the trochanters through the pubic symphysis.

v. Study Visits: Participants in both groups will meet with registered dietitians every 2 to 4 week throughout the Intervention Phase and the dietary intake patterns will be reviewed. A variety of visual tools including food models and common household measuring utensils will be used during the interview to help participants gauge amounts accurately.

a. Assessment will be performed at weeks 0, 2, 4, 6, 8, 12, 16.

1. Vital signs
2. Height
3. Weight
4. Vital Signs
5. Fasting Labs: CBC/Metabolic Panel, Hemoglobin alc, TSH, Cholesterol, TG, HDL, blood sugar, hormone panel (leptin, CCK, GLP-1, PYY, ghrelin, insulin, nesfatin-1)
6. Body Composition and estimated resting metabolic rate
7. Hepatic transient elastography
8. Stool collection for fecal short chain fatty acids and microbiome analysis
9. Satiety Scale
10. 3-Day food record
11. Food frequency questionnaire
12. Adverse Event Tracking

Compliance with consumption will be assessed using check lists that will be turned in during clinical visits. Minimal accepted compliance will be set at 80% of the assigned diet. A participant will be withdrawn once cumulative consumption levels fall to the point that 100% compliance cannot get them over the 80% threshold by the final day of the intervention.

Study Schedule

Procedures	Screen Week -1	Baseline Week 0	Week 2	Week 4	Week 6	Week 8	Week 12	Week 16
Informed Consent	X							
Medical History	X							
Physical Examination	X							
Labs: Serum Pregnancy Test (if needed)	X							
Urine Pregnancy Test (if needed)	X							
Height		X	X	X	X	X	X	X
Weight		X	X	X	X	X	X	X
Vital Signs		X	X	X	X	X	X	X
Labs: CBC/Metabolic Panel, Hormones,		X	X	X	X	X	X	X

Hemoglobin a1c, TSH, lipids							
Body Composition BIA		X	X	X	X	X	X
Liver Stiffness Fibroscan		X	X	X	X	X	X
Product Dispensing		X	X	X	X	X	X
Stool collection		X	X	X	X	X	X
Satiety Scale		X	X	X	X	X	X

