Rationale: In the first aim, we will evaluate whether an isocaloric high protein diets (1 gram of protein per pound of lean body mass) will improve weight loss in comparison to a standard protein diet based on 0.5 gram of protein per pound of lean body mass. Our preliminary studies support the concept that a higher protein meal replacement will result in significant losses of body mass in obese subjects and that a high endogenous level of ghrelin in patients with neuroendocrine tumors results in increased weight gain. In the study, bioelectrical impedance will be used to determine the protein requirement at the level of 0.5 or 1 gram per pound of lean body mass. Weight loss will be the primary outcome. A secondary variable will include satiation as measured using a standard questionnaire, liver stiffness as determined by transient elastography, and microbiome changes determined by 16S sequencing. In addition, we will establish the changes in the levels of the orexigenic peptide ghrelin including the ratio of ghrelin to des-acyl ghrelin, and anorexigenic peptides PYY, leptin, CCK, GLP-1 and nesfatin-1 following high protein meal ingestion.

AIM 2. Characterize the changes in the fecal microbiome induced by a high protein diet

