Recent data suggests that the intestinal microbiome can mediate the response to anti-obesity interventions. Roux-en-Y gastric bypass and vertical banded gastroplasty are associated with long-term alterations of the intestinal microbiome in humans and mice⁽²⁵⁻²⁷⁾. Colonization of germ-free mice with post-bariatric surgery feces resulted in less fat accumulation on standard mouse chow compared to colonization with stool from non-surgical obese patients⁽²⁶⁾. Animal models have highlighted the contribution of *Akkermansia*, a genus that is depleted in obese mice and humans but enriched after gastric bypass surgery^(25,27,28). Colonization of germ-free mice with the microbiome of mice following gastric bypass surgery resulted in weight loss and reduced adiposity compared to recipients of sham operated mice, associated with increased *Akkermansia*⁽²⁷⁾. Daily gavage of live but not heat-killed *Akkermansia muciniphila* reduced adiposity and hyperglycemia in mice with diet induced obesity⁽²⁸⁾. Interestingly, metformin treatment of mice on a high fat diet increases *Akkermansia muciniphila*, which has been proposed as a mechanism of its therapeutic effect⁽²⁹⁾. We recently demonstrated in a rodent model of Western diet-induced obesity that a high protein diet induces *Akkermansia muciniphila*, just as had been seen after bariatric surgery. Abundance of *Akkermansia muciniphila* was inversely correlated with body fat mass. Based on our preclinical rodent model data, we hypothesize that a high protein diet will shift the composition of the microbiome of obese subjects, including increased *Akkermansia*, and that this will result in an altered metagenome (abundances of bacterial genes).

AIM 3. Identify fecal microbial predictors of response to a high protein diet.

Rationale: We hypothesize that subjects will vary in the responsiveness of their microbiota to a HPD based on baseline or post-dietary intervention levels of microbes such as *Akkermansia muciniphila* that respond to the HPD. We will determine the time course of shifts in the microbiome and correlate these changes to weight loss and other metabolic parameters. Further understanding of the link between the microbiome and the beneficial effects of a high protein diet may spur development of therapies for obesity that directly target the microbiome to complement dietary modification.

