two groups. The data for all time points will then be fitted to a multivariate model under a negative binomial distribution using DESeq2 with diet group, time point, interaction between diet and time point, baseline BMI, age, sex, and smoking status as covariates. This model will be compared to a reduced model that does not include the diet:time point interaction⁽⁷⁰⁾. A likelihood ratio test will be used to identify microbes with differential abundance by diet at time points after baseline. Estimates of significance will be adjusted for multiple hypothesis testing⁽⁷¹⁾. OTUs that are differentially abundant on a HPD will be grouped by hierarchical clustering, which we anticipate will highlight distinct kinetic patterns of microbial change.

Expected results/potential pitfalls: We do not anticipate problems with the collection or transportation of fecal samples to our clinical research unit. We predict that *Akkermansia* will significantly increase on a HPD as was seen in our rodent studies. We further predict that most HPD-responsive microbes will have altered abundance within the first 3 to 7 days as has been observed in other dietary studies^(72,73). We estimate a 20% dropout rate based on our high protein meal replacement study, leaving approximately 80 subjects per group. This compares favorably to published studies reporting dietary effects on the microbiome using sample sizes of 10-15^(72,73,74). We anticipate that a HPD will have a similar magnitude of effect as these previously studied diets and hence we expect to have sufficient numbers to detect compositional differences.

2.2 Identification of metagenes affected by a high protein diet.

Experimental protocol: We will assess the functional consequences of altered microbial composition by sequencing the genes carried by intestinal microbes. Shotgun sequencing of DNA extracted from fecal samples will be performed using the HiSeq 3000 with a target depth of 10 GB data per sample, comparable to the 11.7 GB depth used by the Human Microbiome Project for stool samples⁽⁷⁵⁾. Due to the costs of sequencing at this depth, we will only sequence baseline samples and samples from day 112.

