Study design: This is a randomized study using the same subjects described in Aim 1. Nutritional assessment, physical examination, bioelectrical impedance, laboratories will be performed at baseline, and weeks 2, 4, 6, 8, 12 and 16. Stool samples will be collected on day 3, 7, 14, 17, 21, 28, 42, 56, 84 and 112.

Study timeline: Data collection will be completed at week 16. The stool samples collected during the study period will be used for 16S rRNA sequencing, shotgun metagenomics, and data analysis.

Bioinformatics protocol: Patient characteristics (physical measurements, lean body mass, laboratories, demographic traits) at baseline will be compared using a 2-sided t-test (for numerical variables) or chi-square test (for categorical variables) to evaluate the randomization. 3DFR and FFQ performed at each timepoint will be used to assess the predicted protein content of the patient's diet compared to baseline to evaluate the success of the dietary intervention. Clinical response endpoints significantly associated with HPD in Aim 1 will then be correlated with the abundance of microbes found to be enriched or depleted on a HPD in Aim 2.1. These endpoints will be fitted to multivariate models to adjust for baseline clinical covariates including BMI, age, sex, and smoking status. Spearman correlations will then be calculated for all combinations of residuals for the clinical endpoints and for microbial abundance (using DESeq2 fitted multivariate models from Aim 2.1 to adjust for covariates). Separate correlation analyses will be performed at baseline and each of the time points during treatment.

Microbes that are independently associated with clinical response to a HPD will then be used to create random forests classifiers to predict response. Subjects in the HPD group will be identified as responders if they had a decrease in any of the clinical endpoints that exceeded the predictions of the multivariate model for the NPD group. The sensitivity and specificity of the classifiers will be estimated using 10-fold cross-validation. Classifiers constructed from baseline microbial abundance and microbial data at each time point will be compared to determine the earliest time point when accurate predictions of response are possible.

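### Aims 2 and 3 rely on baseline stool, but the plan has no antibiotic or probiotic washout and no dated look-back; the main cost is precision in Aim 3

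*Combined protocol and SAP*

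**What the plan says.** The research plan sets out two microbiome aims, "AIM 2. Characterize the changes in the fecal microbiome induced by a high protein diet" and "AIM 3. Identify fecal microbial predictors of response to a high protein diet". Sections 4.B and 4.C state that both use the Aim 1 subjects, so the Aim 1 eligibility criteria govern them too.

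Those criteria (Section 4.A, items a to m, plus the pregnancy rules) touch on medication twice:

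- Exclusion (j): "Use of any other investigational drug(s) within 8 weeks prior to screening".
- Inclusion (e): "Subjects requiring the regular use of any prescription medication may be admitted to the study providing the dose is stable".

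At screening (Section 4.A, Procedures iv) the practitioner obtains "date of birth, sex, race, medical history, current medications, and smoking and alcohol history". Concomitant medications appear once more, as a safety variable under Secondary Endpoints.

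On the analysis side, the Aim 2.1 model includes "interaction between diet and time point, baseline BMI, age, sex, and smoking status as covariates", and Aim 2.2 sequences metagenomes only at baseline and day 112. For Aim 3, "Classifiers constructed from baseline microbial abundance and microbial data at each time point will be compared". The words antibiotic and probiotic do not occur in eligibility, the stool-sampling instructions or the analysis sections.

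**The concern.** The criteria suit a weight-loss trial. Criterion (j) does not reach marketed antibiotics or over-the-counter probiotics. Criterion (e) concerns regular prescriptions at a stable dose and is silent on a short course that ended before screening. A subject can therefore enter with a baseline sample that does not represent that person's usual flora, and nothing in the required data would reliably show it.

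The plan accepts the general principle elsewhere. It requires stable smoking habits and adjusts the microbiome models for smoking. Its background also cites a marketed drug, metformin, as raising *Akkermansia* in mice, the genus expected to rise on the high protein diet. No medication term enters any microbiome model.

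At stake is the precision of Aim 2 and, more directly, how well baseline abundance can predict response in Aim 3. The plan also does not say how stool collected after a course taken during the 16 weeks is to be treated.

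**Working it through.** The plan states no figure on this point, so there is none to reproduce. The check has three parts.

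**1. Where baseline stool enters the inference.**

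- Aim 2.1: a between-arm comparison of baseline abundance, then a likelihood ratio test of the diet-by-time interaction.
- Aim 2.2: baseline against day 112 only. With two time points, an atypical baseline cannot be recognised from a subject's trajectory.
- Aim 3: correlations at baseline and at each later time point, and random forest classifiers, some built on baseline abundance.

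**2. Effect on the Aim 2 diet-by-time contrast.** Let a share f of subjects be recently exposed, and let their abundance move by r(t) between baseline and time t as the disturbance resolves. Under 1:1 randomization the expected extra change is f × r(t) in each arm, so the expected difference between arms is f × r(t) − f × r(t) = 0. The shared movement falls on the time main effect, which stands in both the full and the reduced model. Simulated change scores at 80 per arm, with no diet effect and the assumed exposures below, gave bias of about zero and a type I error close to the nominal 5%.

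What remains is noise and chance imbalance.

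**3. Size under stated assumptions.** From the plan: 200 subjects, 100 per arm and 20% dropout, so 100 × 0.80 = 80 per arm, as Section 4.B says. Assumed: f = 5-20% (200 × 0.05 = 10 to 200 × 0.20 = 40 subjects) and a shift s = 1-2 SD in a taxon's abundance.

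Write observed baseline abundance as X = U + sZ. U is usual abundance with SD 1. Z is 1 if exposed (probability f) and 0 otherwise, independent of both U and the clinical response Y. Then:

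- Var(X) = v = 1 + f(1 − f)s²
- Cov(X, Y) = Cov(U, Y), so corr(X, Y) = corr(U, Y) / √v
- effective n per arm = 80 / v
- power for a 0.5 SD difference in means, two-sided 5%, normal approximation = Φ(0.5 × √(40/v) − 1.96)

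| f | s | v | 1/√v | Loss in correlation | Effective n per arm | Power |
|---|---|---|---|---|---|---|
| none | – | 1 | 1 | 0% | 80 | 0.89 |
| 5% | 1 | 1 + 0.0475 × 1 = 1.048 | 0.977 | 2% | 76 | 0.87 |
| 10% | 1.5 | 1 + 0.09 × 2.25 = 1.203 | 0.912 | 9% | 67 | 0.82 |
| 20% | 2 | 1 + 0.16 × 4 = 1.64 | 0.781 | 22% | 49 | 0.69 |

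The power column illustrates a comparison of means, not the plan's negative binomial test.

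For chance imbalance, take exposed counts as binomial with n = 80 in each arm. The probability that the arms differ by 5 or more exposed subjects is 10% at f = 5%, 23% at f = 10% and 37% at f = 20%.

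**The case against.** The strongest reply is randomization. A reader might infer that recovery after antibiotics would pass for a diet effect in the Aim 2.1 test. The documents do not support that: assignment is 1:1, shared recovery is absorbed by the time effect, and the test already allows for chance imbalance. Aim 2.1 also plans a baseline comparison between arms, which could show an imbalance in flora, though not that an individual baseline is atypical. This part of the reply stands.

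A reader might also infer that past courses are beyond recovery. That goes too far. Screening takes "medical history, current medications, and smoking and alcohol history", and a treated infection may be noted there. What can be said is that no dated look-back is required, so completeness cannot be assumed. For use during the study, the concomitant-medication record already exists; what is missing is a rule linking it to stool samples.

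A third inference is that Aim 3 is confounded. That would need prior antibiotic use to affect clinical response as well as flora, and nothing in the documents shows this. The calculation above models attenuation only. It can also be argued that abundance as found at entry is the intended predictor, and that excluding recent users narrows the population to which a classifier applies. That is a genuine trade-off and belongs among the costs.

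Finally, the size rests wholly on assumed inputs, and its low end is negligible. That is correct. No size is offered for probiotics.

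**Conclusion.** The gap is real: following the plan as written admits recently treated subjects, and analysts cannot reliably identify them afterwards. Its consequence is loss of precision. For Aim 2 this means added noise and chance imbalance, not systematic bias. For Aim 3, where randomization does not protect the link between baseline abundance and response, a true correlation would be attenuated by about 2-22%, and by about 9% at 10% exposure and a 1.5 SD shift.

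These figures depend on the assumed exposure share and shift, and on exposure being unrelated to usual flora and to response. A reader might extend the concern to the main trial result, but weight loss at 16 weeks is the primary outcome and the basis of the sample size, and it does not depend on stool data. This is a cheap improvement for two of three aims, not a threat to the primary comparison.

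**What to change.** 1. Add to the Section 4.A exclusion criteria a deferral for systemic antibiotics or probiotic supplements within a prespecified window before the baseline stool, with re-screening allowed once the window has passed. The investigators should set and justify its length. The 8 weeks in criterion (j) was written for investigational drugs and is only a starting point.
2. Add one dated question on antibiotic and probiotic use to the screening history in Procedures iv.
3. Prespecify, for Aims 2 and 3, a sensitivity analysis that omits stool collected after an on-study course, identified from the concomitant-medication record already planned.

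The window needs a defined baseline sample. The visit assessments list stool at week 0, whereas the stool sampling days in the Fecal Sampling text and in Sections 4.B and 4.C begin at day 3; these passages should be reconciled at the same time.

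The cost is one criterion, one question and a repeated analysis, with no new procedure. Some volunteers will be deferred; on the assumed range that could be up to 20%, depending on the window, against a planned accrual of 3-4 years. The microbiome results will then apply to subjects without recent exposure, and the report should say so.
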